9.1.4. Early Termination Visit

Patients who withdraw consent during either part of the study will be asked to return to the clinic for an early termination visit. For patients in Part 1, this will consist of the EOT1/early termination assessments described in [Table 2](#). For patients in Part 2, this will consist of the EOT2/early termination assessments described in [Table 3](#). Procedures regarding discontinuation for other reasons are described in [Section 9.1.5](#).

9.1.5. Visit Schedule for Patients Who Discontinue Study Drug

9.1.5.1. Visit Schedule for Patients Who Discontinue Neoadjuvant Cemiplimab

Patients who permanently discontinue from neoadjuvant study drug due to disease progression (per RECIST 1.1; [Appendix 4](#)) or toxicity will undergo surgery (if clinically appropriate) and will return for post-surgical follow-up visit (EOT1). These patients must be followed for 90 days after last dose of cemiplimab for AE identification and reporting and are ineligible to receive adjuvant cemiplimab.

Patients who discontinue neoadjuvant therapy but achieve complete resection of all macroscopic disease (R0 or R1 resection) and who do not withdraw consent from the study will subsequently be followed by imaging per the schedule in [Table 3](#) (imaging at week 15 of Part 2 (± 10 days), week 30 (± 10 days), and week 48/EOT2 followed by imaging per the schedule in [Table 4](#) (every 4 months for the first 2 years and every 6 months for the third year), or until disease recurrence, whichever occurs first. Patients who undergo R2 surgical resection (residual gross disease) will be followed for survival only.

9.1.5.2. Visit Schedule for Patients Who Discontinue Adjuvant Cemiplimab

Patients who discontinue cemiplimab prior to the completion of the adjuvant dosing schedule due to unacceptable toxicity or reasons other than disease recurrence will be assessed by imaging only at week 15 of Part 2 (± 10 days), week 30 (± 10 days), and week 48/EOT2 or until disease recurrence, whichever occurs first. Week 0 is defined as 3 weeks (± 3 days) after the EOT1 visit.

Patients who discontinue adjuvant cemiplimab due to toxicity or reasons other than disease recurrence but complete the week 48/EOT2 evaluation visit without disease recurrence will enter follow-up. During follow-up they will undergo imaging assessments every 4 months for the first 2 years and every 6 months for the third year.

Patients who permanently discontinue from study drug due to disease recurrence (see [Section 9.2.2.4](#)) will be asked to return for an EOT2/early termination visit and will be subsequently followed for survival.

9.1.6. Visit Schedule for Patients Who Receive Adjuvant Radiation Therapy or Observation Only

After surgery, management options include adjuvant cemiplimab, adjuvant radiation therapy, or observation only. A patient who receives adjuvant radiation therapy will not receive adjuvant cemiplimab (neither sequentially nor concurrently) during the study.

Patients who undergo adjuvant radiation therapy or enter observation only during Part 2 of the study will be assessed by imaging only, at week 15 (± 10 days), week 30 (± 10 days), and week 48 (± 10 days) (corresponding to the equivalent EOT2 visit for patients receiving cemiplimab). Week 0 is defined as 3 weeks (± 3 days) after the EOT1 visit. Other assessments listed in [Table 3](#) are not required for a patient who receives adjuvant radiation therapy or observation only. However, biopsy should be attempted for all patients in the event of suspected recurrence or suspected SPT as described in [Section 9.2.2.7](#).

Patients who complete the week 48 evaluation visit without disease recurrence will enter follow-up, in which they undergo imaging assessments every 4 months for the first 2 years and every 6 months for the third year.

Details regarding the adjuvant therapy received by an individual patient will be reported in the eCRF (Section 12).

9.1.7. Survival Follow-Up

Survival follow-up begins after completion of the follow-up schedule of events in Table 4 (including patients who follow an imaging schedule), or after disease recurrence. Any patient who fails to achieve complete surgical resection (defined as R0 or R1) will also enter survival follow-up. Patients in survival follow-up will be contacted quarterly (telephone is acceptable) for survival status and treatment status (subsequent anticancer systemic therapy) until the EOS.

9.1.8. Unscheduled Visits

All attempts should be made to keep patients on the study schedule. Unscheduled visits may be necessary to repeat testing following abnormal laboratory results, for follow-up of AEs, or for any other reason, as warranted.

9.2. Study Procedures

9.2.1. Procedures Performed Only at the Screening/Baseline Visit

The following procedures will be performed for the sole purpose of determining study eligibility or characterizing the baseline population:

- Serum β -HCG (test must be done ≤ 72 hours before the first dose)
- HBV, HCV, and HIV screening
- Height measurement
- Recording of medical history/oncology history

9.2.2. Efficacy Procedures

The primary endpoint is pCR in the surgical pathology sample after neoadjuvant therapy, according to an independent central pathology review committee. The secondary endpoint regarding changes to planned surgery or radiation therapy will be assessed according to an independent surgical review committee. Secondary endpoints regarding response rate per RECIST 1.1 prior to surgery and regarding disease-free survival after surgery require imaging studies.

9.2.2.1. Pathologic Assessment of Tumor Response

An independent central pathology review committee will assess pCR rate and mPR rate (Section 6.3.1). A complete description of the procedures will be provided in a separate charter.

9.2.2.2. Change in Surgical Plan and Post-Surgical Management (Treatment Management Plan Assessment)

During the screening period, the investigator will report what the management plan would be regarding surgery and post-surgery (including adjuvant radiation, if applicable) if the patient had not been enrolled in the clinical trial. After completion of neoadjuvant cemiplimab, the investigator will report the actual surgery that was performed. If adjuvant radiation therapy is administered, details will be reported. See Section 5.2.2 for study variables regarding surgical plan and post-surgical management.

9.2.2.3. Imaging Studies

Imaging studies are required for secondary endpoints regarding response rate per RECIST 1.1 (Eisenhauer, 2009) (Appendix 4) prior to surgery in Part 1 of the study and regarding disease-free survival after surgery in Part 2 of the study.

Regarding baseline imaging requirements:

- For patients with non-HN primaries, baseline imaging should be CT scan of the chest/abdomen/pelvis with iodinated contrast. Magnetic resonance imaging (MRI) with gadolinium is acceptable for the abdomen/pelvis. Additional CT or MRI imaging will be obtained for lesions of interest, as clinically indicated (ie, radiologic imaging of extremity for patients with CSCC of extremity).
- For patients with HN primaries, CT neck with iodinated contrast (and/or MRI neck with gadolinium) is required and CT chest is required. If patient has CSCC lesions of the head that are not imaged adequately by neck CT or MRI neck, additional baseline radiologic imaging of the head should be obtained as appropriate. Lesions of interest identified in screening should be re-imaged at subsequent assessments.
- In Part 1, digital photography is mandatory at baseline imaging assessment and at the imaging assessment that occurs prior to surgery; photography at imaging assessment prior to the third dose is optional. Radiologic imaging is required at each imaging assessment in Part 1 and Part 2. Digital photography is optional for imaging assessments in Part 2. Radiologic imaging of externally visible lesions can be supplemented with digital medical photography and such clinical imaging may inform response assessments per RECIST 1.1 (Eisenhauer, 2009)(Appendix 4). Guidelines for digital medical photography are provided in Appendix 5. However, photography will not replace radiologic imaging. Radiologic imaging at each of the protocol-specified timepoints is required even if optional photography is performed.

For each postbaseline (post-screening) imaging assessment for a given patient (from screening through recurrence), the investigator should, whenever possible, be consistent with the radiologic imaging methods that were used during screening for that patient.

During Part 1 of the study (neoadjuvant), imaging assessments are planned after the 2nd and 4th doses of cemiplimab. During Part 2 of the study (adjuvant), imaging is performed approximately every 15 weeks to monitor disease recurrence during the treatment period. There is a subsequent follow-up period of 3 additional years, to provide approximately 4 years total follow-up after surgery. The vast majority of advanced CSCC recurrences occur within 2 years after surgery, with a small number of additional recurrences in year 3 after surgery (Porceddu, 2018).

The required imaging assessments are shown in the schedules of events in Table 2, Table 3, and Table 4. Additional imaging may be obtained at an earlier time point than required in the schedules of events if clinically indicated in the opinion of the investigator. Unscheduled assessments would be reported in the eCRFs but would not substitute for the next required imaging assessment in the protocol schedule of events. Positron emission tomography (PET) imaging is not required in the study. However, the results of any PET imaging performed as standard of care during the study will be reported in eCRFs as supplemental information.

Brain imaging is not mandatory at baseline or at subsequent assessments. However, if the investigator feels that there is a clinical suspicion of brain metastases at any time, appropriate brain imaging should be obtained.

At the sponsor's discretion, de-identified imaging studies (scans and photographs) may be collected and reviewed by independent radiologists and/or other qualified reviewers at a later date, or at any time during the study.

9.2.2.4. Characterization of New Skin Lesions (Disease Recurrence) or SPT Following Surgery

In CSCC, the most common sites of metastases are lymph node and lung (Hillen, 2018). New CSCC lesions in the skin usually are not metastatic lesions. With rare exceptions, new CSCC lesions in the skin are new primary tumors due to field cancerization from chronic UV-mediated skin damage (Christensen, 2018). In a previous randomized trial in advanced CSCC, recurrent skin disease and SPTs were recognized as distinct entities (Brewster, 2007). In this study, SPTs are non-metastatic CSCC lesions in the skin that can be managed by local modality therapy as part of routine clinical practice.

However, there are 2 circumstances in which a new skin lesion in a CSCC patient could represent metastatic disease:

- Epidermotropic metastases (EDMs), defined as distant lesion(s) in the dermis without epidermal involvement (Skala, 2018)(Weidner, 1985). Although EDM are well described in the melanoma literature, this would be a highly atypical pattern of recurrence in patients with CSCC. However, EDM could occur in a CSCC patient because cutaneous metastases from squamous cancers arising in internal organs have been described (Bornkessel, 2006)(Plataniotis, 1999).

NOTE: In the event of a new rapidly growing CSCC lesion involving both dermis and epidermis that is not appropriate for local modality treatment and requires new systemic therapy, this should be designated as an EDM, not an SPT.

- In-transit metastases (ITMs) are defined as cutaneous nodule(s) distinct from the primary tumor and occurring proximal to the first lymph node basin (Xu, 2018). Of note, not all CSCC lesions arising in the skin proximal to the first lymph node basin are ITM. Due to chronic sun exposure, new lesions in sun-exposed skin may represent SPTs. The decision about whether to call such a lesion an SPT or an ITM will be based on the overall clinical presentation of the lesion. These ITMs are most often subcutaneous or dermal papules with occasional exophytic features (Carucci, 2004). The investigator will indicate in source documents and eCRF pages the basis for designating a new skin CSCC lesion as ITM or SPT.

In this study, a new CSCC lesion arising on the skin during the study period will be classified as an SPT unless the lesion represents ITM or EDM. Second primary CSCC tumors are not counted as events for the DFS endpoint. Patients who develop ITM or EDM will be considered to have experienced a DFS event.

Second primary CSCC tumors arising during the study period should be treated with surgery or another permitted local modality. Permitted non-surgical local modalities for SPTs in this study are: topical 5-fluorouracil, topical imiquimod, and photodynamic therapy with topical aminolevulinic acid or methyl aminolevulinate (Christensen, 2018).

For any cutaneous lesion that is resected during the course of the study, the following information will be captured in eCRF pages: histologic diagnosis, maximum diameter, and investigator's impression regarding whether lesion represents SPT or a disease recurrence (either ITM or EDM). The reason the investigator deems a lesion to be SPT or recurrence will be documented in eCRF.

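### Read literally, Protocol 9.2.2.4 codes a locally treatable skin recurrence at the resection site as a second primary tumor, although the DFS definition counts local recurrence

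*Protocol*

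**What the plan says.** Protocol 9.2.2.4 sorts skin lesions that appear after surgery. By default, a "new CSCC lesion arising on the skin during the study period will be classified as an SPT unless the lesion represents ITM or EDM". It adds that "Second primary CSCC tumors are not counted as events for the DFS endpoint", while ITM and EDM do count. For a cutaneous lesion resected during the study, the eCRF is to hold the investigator's "impression regarding whether lesion represents SPT or a disease recurrence (either ITM or EDM"), together with the reason for the call.

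The same section describes the categories:

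- SPT: "SPTs are non-metastatic CSCC lesions in the skin that can be managed by local modality therapy as part of routine clinical practice".
- ITM: a skin nodule "distinct from the primary tumor and occurring proximal to the first lymph node basin". No distance is given.
- EDM: a distant lesion confined to the dermis. A note adds a rapidly growing lesion of dermis and epidermis if it is "not appropriate for local modality treatment and requires new systemic therapy, this should be designated as an EDM, not an SPT".

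Other sections treat local recurrence as an event:

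- Protocol 5.2.1 and SAP 4.4.2 name local recurrence among the DFS and EFS events after R0 or R1 resection.
- Protocol 9.2.2.5 describes recurrence as one or more new CSCC lesions that may be local, and gives the investigator a local option in the eCRF. Its own ITM definition requires more than 2 cm from the primary lesion.
- Protocol 9.2.2.6 gives a date rule for recurrence shown by pathology alone, with skin disease as an example.

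SAP 4.4.2 does not mention SPTs.

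**The concern.** The rule in 9.2.2.4 is closed: a new skin lesion is an SPT unless it is one of two named things, and local recurrence is not one of them. The resected-lesion eCRF item repeats this by equating recurrence with ITM or EDM. No text says which section controls when this rule meets the DFS definition.

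A site that follows 9.2.2.4 to the letter would leave a locally treatable skin relapse at the resection site out of DFS. A site that follows 5.2.1, 9.2.2.5 and 9.2.2.6 would count it. With about 20 sites, the DFS estimate could mix two definitions. The DFS population includes R1 resections, that is, positive microscopic margins, so regrowth at the site is a failure that DFS ought to capture.

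**Working it through.** The plan states no DFS or EFS figure to reproduce. The check is a comparison of texts, followed by an illustration of size.

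**Step 1: test one lesion against the rule.** Take a CSCC lesion on the skin at the resection site that can be treated locally.

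| Test | Met? | Why |
|---|---|---|
| New lesion on the skin (9.2.2.4) | Yes | 9.2.2.5 itself calls local recurrence a new CSCC lesion, so the word new does not exempt it |
| ITM (9.2.2.4) | No, read literally | It must be distinct from the primary |
| ITM (9.2.2.5) | No | It must be more than 2 cm from the primary |
| EDM | No | It must be distant and dermal only |
| EDM note | No | The lesion is suitable for local treatment |
| SPT description | Fits | Non-metastatic and locally managed; no distance from the scar is required |

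Result under 9.2.2.4: SPT, not a DFS event. Result under 5.2.1 and SAP 4.4.2: local recurrence, a DFS event. The two cannot both be followed.

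**Step 2: scope.** The rule covers only lesions arising on the skin. The SPT exclusion is written for DFS. EFS is reached only because a lesion coded SPT would not be recorded as a recurrence.

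**Step 3: illustration of size.** Every input below is an assumption for the trial population. Protocol 3.2.4 gives 3-year risks of >15% (local) and >10% (nodal) for node-negative stage III. I set the risks at those lower bounds, treat them as independent, and ignore censoring.

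- 3-year DFS with all local recurrences counted: (1 − 0.15) × (1 − 0.10) = 0.765.
- Let f be the share of local recurrences that are locally treatable skin lesions, times the share of those coded SPT. DFS becomes (1 − 0.15(1 − f)) × 0.90, a rise of 0.15 × 0.90 × f = 0.135f.

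| Both shares | f | Rise in DFS (points) | Patients, of at most 76 |
|---|---|---|---|
| 25% | 0.0625 | 0.8 | 0.6 |
| 50% | 0.25 | 3.4 | 2.6 |
| 75% | 0.5625 | 7.6 | 5.8 |
| 100% (extreme, not expected) | 1 | 13.5 | 10.3 |

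At f = 0.25, a local risk of 10% gives 0.10 × 0.90 × 0.25 = 2.25 points, and 20% gives 4.5.

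For scale, the 95% CI half-width at 76.5% with 76 patients is 1.96 × √(0.765 × 0.235 / 76) = 0.095. The rise exceeds it only if f is above 0.0953 / 0.135 = 0.71. DFS is limited to R0/R1 patients, so 76 is a ceiling.

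**The case against.** The best defence is that 9.2.2.4 separates new primaries from metastases and never meant to reach relapse of the resected tumor. A relapse is not a second primary, and the section itself recalls an earlier trial in which "recurrent skin disease and SPTs were recognized as distinct entities". This is probably what was intended. It does not override the explicit rule or the matching eCRF item, and the judgment that 9.2.2.4 describes is between SPT and ITM only.

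Three further points stand and limit the effect:

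- **Other routes to an event.** For head-and-neck tumors, 9.2.2.5 counts nodal or soft-tissue relapse above the clavicle as locoregional recurrence, and Protocol 1.1 says that most CSCC arises there. The clause does not name skin. For other sites, the text covers the first draining nodal basin and ITM but not the tumor bed. The ITM wording in 9.2.2.4, which has no distance limit and leaves the call to clinical presentation, might also be stretched to a nodule near the scar.
- **Traceability.** "The investigator will indicate in source documents and eCRF pages the basis for designating a new skin CSCC lesion as ITM or SPT". For resected lesions the reason for an SPT or recurrence call is also recorded, with histology and maximum diameter. Biopsy information is kept (9.1.2, 9.1.3), and scans and photographs may be reviewed independently (9.2.2.3). Partial reclassification may therefore be possible.
- **Role of the endpoints.** DFS and EFS are secondary and descriptive, with no test.

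**Conclusion.** The conflict is real and worth fixing: followed as written, 9.2.2.4 gives a locally treatable skin recurrence at the resection site the wrong DFS classification. This conflict can only take DFS events away. Its size cannot be derived from the documents. The illustrative 0.8 to 7.6 points rest on background risks for one stage group and on two shares with no source, and all lie inside the approximate CI half-width of 9.5 points.

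A reader might infer more than the documents support:

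- **That local recurrences in general are lost.** They are not. Deep or imaging-detected recurrences fall outside the rule, and investigators have competing text under which to code an event.
- **That SPTs are excluded from EFS.** No passage says so; the effect on EFS is an inference.
- **That the eCRF cannot show where a lesion lay.** The protocol lists no field for location relative to the scar, but the eCRF is not among the documents.
- **That every related gap favors fewer events.** The looser ITM definition in 9.2.2.4 could add events relative to 9.2.2.5.
- **That the trial's main conclusion is at risk.** The primary pCR analysis is untouched.

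**What to change.** Reconcile the passages for endpoint classification only, leaving clinical management to the investigator:

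1. In Protocol 9.2.2.4 and its resected-lesion eCRF item, extend the exceptions to local recurrence, ITM or EDM. Investigator judgment stays.
2. Use one ITM definition in 9.2.2.4 and 9.2.2.5.
3. In SAP 4.4.2, state the SPT rule once and apply it to both DFS and EFS.

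The cost is a few words of protocol text, one eCRF option and a few SAP sentences. The downside is that some true new primaries near the scar may be counted as events.

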9.2.2.5. Definitions for Patterns of Disease Recurrence Following Surgery

The pattern of treatment failure, as manifested by disease recurrence, is defined as ≥ 1 new CSCC lesion(s), either local, regional, or distant. Definitions of locoregional and distant recurrences are provided in this section.

- **Locoregional recurrence:** Any of the following sites of disease recurrence:
 - For HN CSCC, nodal or soft tissue recurrence above the clavicle.
 - For non-HN CSCC, recurrence within the first draining nodal basin (or soft tissue associated within the first draining nodal basin) of the resected tumor.
 - In-transit metastases, defined as skin or subcutaneous metastases that are >2 cm from the primary lesion but are not beyond the regional nodal basin.
- **Distant recurrence:** Any of the following sites of disease recurrence:
 - For HN CSCC, nodal recurrence below the clavicle.
 - For non-HN CSCC, recurrence beyond the first draining nodal basin of the resected tumor bed. Recurrence in 2 nodal basins will be considered distant recurrence, even if contiguous (ie, 2 mediastinal nodal basins, 2 pelvic nodal basins).
 - Recurrence in non-nodal tissue (including, but not limited to, lung, liver, bone, brain).

- Epidermotropic metastases, defined as distant lesion(s) in the dermis without epidermal involvement.

For all recurrences, the investigator will indicate in the eCRF page whether recurrent disease for an individual patient at the time of first recurrence is local, regional, distant or a combination (concurrent locoregional + distant recurrences).

9.2.2.6. Date of Disease Recurrence Following Surgery

The date of disease recurrence is captured in the eCRF by the investigator. Evidence of recurrence on imaging should be confirmed with a biopsy to obtain histologic or cytologic evidence of CSCC in all cases of suspected disease recurrence, unless biopsy is considered to pose an unacceptable safety risk in the opinion of the investigator (eg, brain lesions) (Section 9.2.2.7).

The date of disease recurrence is the first date when recurrence is observed, as defined in the following clinical situations:

- **Radiologic Evidence with Confirmatory Pathology Sample:** The investigator obtains both imaging and pathologic confirmation of recurrent disease. If the pathology sample is obtained prior to the imaging, the date of the procedure to obtain the pathology sample will be the date of recurrence. If the pathology sample is obtained after the imaging, and if the biopsy procedure date is within 21 days of the imaging date, the recurrence date will be the date of the imaging assessment that was done prior to the procedure to obtain the pathology sample. **Whenever possible, pathologic confirmation of the radiologic recurrence should be obtained unless in the judgment of the investigators, there are clinical circumstances that result in an unacceptable safety risk associated with biopsy for a patient.**

Note: If the procedure date that confirms pathologic recurrence is performed more than 21 days after the most recent imaging, the biopsy procedure date (not the imaging date) will be the date of recurrence. This 21-day rule is to guard against retroactively declaring progression based on equivocal radiologic findings that were not considered to be progression at the time that the imaging was obtained, in view of the fact that study drug is administered every 21 days.

- **Pathologic Evidence Only:** A procedure was performed to obtain a pathology sample to establish disease recurrence, but there is no corresponding imaging. Generally, imaging should be performed in the setting of recurrent disease. However, if a clinical circumstance arises in which there is only histologic (pathologic) confirmation of recurrence (eg, recurrent disease on the skin or palpable node for which imaging was not obtained due to logistical reasons) or if the imaging is more than 21 days prior to the procedure date (see note in bullet immediately above), the biopsy procedure date is the date of disease recurrence that is captured in the eCRF page.

- **Radiologic Evidence Only:** Only imaging was obtained (eg, a patient with radiologic evidence of recurrence in which the investigator feels that biopsy would pose an unacceptable safety risk due to location of the lesion or other clinical considerations). In this case, the imaging date will be the date of disease recurrence that is captured in the eCRF page. If a prior scan had equivocal findings that were not considered to establish recurrence (and biopsy was not obtained), and the subsequent scan is felt to establish evidence of recurrence (but biopsy cannot be obtained due to safety reasons), the date of the subsequent scan will be the date of recurrence in the eCRF page.

